7.1.2 Goal Attainment Scaling (GAS)

Domains: Three individualized goals per participant

- Behavior
- Engagement/Participation
- Resilience

Scoring: -2 (much worse than expected) to +2 (much better than expected outcome) **Frequency:**

Weekly observations during both intervention and control periods **Conversion:** Raw scores converted to T-scores (M=50, SD=10) for statistical analysis

7.2 Data Collection Schedule

Assessment Period	IG1	IG2	Measures
Baseline (Week 0)	X	X	All standardized measures, initial GAS
Week 6/7	X	X	All standardized measures
Week 14	X	X	All standardized measures
Weekly	X	X	GAS observations

8. Statistical Analysis Plan

8.1 Sample Size Justification

This pilot study was powered based on available population at the ELC (n=40 maximum enrollment). Post-hoc power analyses indicated observed power below 20% for standardized measures due to small sample sizes, despite meaningful effect sizes. Future studies require:

- PROMIS Flexibility (d=0.68): 21 participants per group for 80% power
- PROMIS Persistence (d=0.63): 25 participants per group for 80% power
- PedsQL Social Functioning (d=0.53): 35 participants per group for 80% power

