8.2 Statistical Methods

8.2.1 Primary Analysis - Standardized Measures

Baseline Comparisons: Independent samples t-tests for continuous variables to assess randomization success

Primary Efficacy Analysis: Analysis of Covariance (ANCOVA)

- Independent Variable: Group assignment (IG1 intervention vs. IG2 waitlist control)
- Dependent Variables: Week 7 standardized assessment scores
- Covariates: Baseline scores, any maturation effects identified in IG2 waitlist period
- Effect sizes: Cohen's d with 95% confidence intervals

Secondary Analysis: Paired samples t-tests for within-group changes

- One-tailed tests for intervention effects (directional hypotheses)
- Two-tailed tests for control period effects

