8.3 Missing Data Handling

Approach: Listwise deletion for each analysis **Rationale:** Participants included only with complete baseline and outcome data for each specific measure **Impact:** Sample sizes range from n=17-19 for primary ANCOVA analyses (8-10 participants per group)

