8.4 Significance Level

Alpha set at 0.05 for all analyses

9. Data Management

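### The observed-power sentence in section 8.1 only restates a large p-value, so it cannot support a meaningful effect missed through small numbers over no effect

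*Combined protocol and SAP*

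**What the plan says.** Section 8.1 (Sample Size Justification) bases the sample size on the number of children available at the centre, then reports: "Post-hoc power analyses indicated observed power below 20% for standardized measures due to small sample sizes, despite meaningful effect sizes". It goes on to list sizes for future studies, including "PROMIS Flexibility (d=0.68): 21 participants per group for 80% power" and "PROMIS Persistence (d=0.63): 25 participants per group for 80% power"; the third entry is PedsQL Social Functioning at d=0.53. No interval accompanies these d values, and the method behind the power figure is not given.

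Section 8.3 gives the numbers analysed: "Sample sizes range from n=17-19 for primary ANCOVA analyses (8-10 participants per group". Section 8.4 says: "Alpha set at 0.05 for all analyses". Section 8.2.1 names the main comparison of week 7 scores ("Primary Efficacy Analysis: Analysis of Covariance (ANCOVA") and plans "Effect sizes: Cohen's d with 95% confidence intervals". It specifies "One-tailed tests for intervention effects (directional hypotheses" only for the secondary paired tests; the sidedness of the ANCOVA is not stated.

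**The concern.** The sentence does two things. It explains low power by sample size, and it calls the effects meaningful. Read together, these invite the conclusion that the programme worked on the standardized measures and that only the number of children stopped the trial from showing it.

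The evidence offered is power computed from the observed effect. Once the sample size and alpha are fixed, that quantity contains nothing that the p-value does not. A low value says the result was far from significant, which is expected both when a real effect is studied in too few children and when there is no effect. Calling the estimates meaningful does not separate the two, because no interval is used.

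The standardized battery is listed as primary in section 7.1, and section 15.1 plans to publish primary efficacy results. At stake is whether a non-significant result there is described as inconclusive or as a benefit hidden by sample size.

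**Working it through.** **Inputs.** Analysed groups of 8-10, total 17-19 (section 8.3); alpha 0.05 (section 8.4); d = 0.53, 0.63, 0.68 (section 8.1). Assumed, because not stated: a two-sided test and, except where noted, no baseline adjustment.

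**Formulas.** Let k = √(1/n₁ + 1/n₂). The test statistic is t = d/k on n₁+n₂−2 degrees of freedom. Power is the probability that a noncentral t with noncentrality d/k falls outside ± the critical value. At 9+9, k = 0.471, df = 16 and the critical value is 2.120.

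**Step 1. The plan's own figure.** Power at the listed d values:

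| d | 8+9 | 9+9 | 9+10 |
|---|---|---|---|
| 0.53 | 0.176 | 0.185 | 0.193 |
| 0.63 | 0.229 | 0.242 | 0.253 |
| 0.68 | 0.259 | 0.274 | 0.287 |

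Only d=0.53 falls under 20%. One-sided power is higher (0.27-0.41). Using the ANCOVA degrees of freedom (15) at 9+9, with no gain in precision, gives 0.184, 0.240 and 0.272. The stated figure is therefore not reproduced for two of the three effects.

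**Step 2. What observed power under 20% means.** Solve for the observed t at which power, with noncentrality set to that t, equals 0.20:

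| | 8+9 | 9+9 | 9+10 |
|---|---|---|---|
| t | 1.190 | 1.185 | 1.180 |
| d = t × k | 0.578 | 0.559 | 0.542 |
| two-sided p | 0.253 | 0.253 | 0.254 |

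Observed power under 20% is the same event as p above about 0.25.

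**Step 3. How often one scale meets it.** The probability that |t| is below the step 2 value:

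| True d | 8+9 | 9+9 | 9+10 |
|---|---|---|---|
| 0 | 0.747 | 0.747 | 0.746 |
| 0.53 | 0.517 | 0.504 | 0.492 |
| 0.63 | 0.443 | 0.427 | 0.413 |
| 0.68 | 0.405 | 0.388 | 0.373 |

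On a single scale the criterion is met more often with no effect than at any of the listed effects. A one-sided test gives 0.793 with no effect.

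**Step 4. The listed effects with intervals.** At 9+9, unadjusted, with the 95% interval from inverting the noncentral t:

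- d=0.53: t = 0.53/0.471 = 1.12, p = 0.28, interval −0.42 to 1.46
- d=0.63: t = 1.34, p = 0.20, interval −0.33 to 1.57
- d=0.68: t = 1.44, p = 0.17, interval −0.28 to 1.62

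All three include zero. If the d values come from adjusted means, a baseline correlation ρ divides t's denominator by a further gain: t = d/(k√(1−ρ²)). With ρ=0.7 and d=0.68, t = 0.68/(0.471 × 0.714) = 2.02, still below the critical 2.13 on 15 df.

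**Step 5. What the design can detect with 80% power.** Unadjusted: d = 1.457 (8+9), 1.407 (9+9), 1.366 (9+10). With ANCOVA the noncentrality is d/(k√(1−ρ²)) on n₁+n₂−3 df. At 9+9 this gives d of about 1.35, 1.22 and 1.01 for ρ = 0.3, 0.5 and 0.7. Across 17-19 children and that range of ρ, d runs from about 1.0 to 1.4. The documents do not give ρ.

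**The case against.** Several points on the other side stand.

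- **The sample really is small.** Step 1 shows power of about 18-29% at the listed effects. As a fact about the design, low power is true.
- **The wording is narrower than it may seem.** A reader might infer that section 8.1 blames weak results on sample size, or claims a benefit. Literally, it explains low power; it states no efficacy conclusion and no p-value, and no decision rule in the plan uses observed power. The interpretation enters through the clause about meaningful effects.
- **The 75% is easily over-read.** It applies to one scale and one two-sided test, and ignores the sign. Counting only estimates in the programme's favour, it is about 0.37. All measures falling under 20% together with no effect is less likely: about 42-54% for three measures and 7-30% for nine, at assumed correlations of 0-0.7. Nor is it the rate of a favourable d of at least 0.53 together with observed power under 20%, which is only 0.5-2.0% on one scale with no effect.
- **The 0.25 cut-off depends on an assumed method.** Two of the three listed effects do not fit the stated figure under that method. The one-to-one link between observed power and p does not depend on it.
- **The replacement rule is not sharper.** At 9+9 unadjusted, an interval including zero occurs 95% of the time with no effect, and also about 73-82% of the time at a true d of 0.68-0.53. It does not let a null result count against the programme; it only avoids claiming more than the data show.

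None of this makes observed power informative about why the results were not significant.

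**Conclusion.** The point holds as a matter of interpretation. For a single two-sided 0.05 test with 8-10 per group, observed power under 20% means p above about 0.25. That occurs on about 75% of scales with no effect and, at 9 per group, on 39-50% at a true d of 0.68-0.53. The sentence gives no support to a meaningful effect missed through small numbers over no effect, and the listed d values do not supply that support either.

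A reader might go further and infer that the programme has no effect, or that sample size is not a problem. The documents support neither: unsupported is not the same as false, and power is low for effects of the size listed. The figures rest on a two-sided test and, except where shown, no baseline adjustment. The design, the data and the planned estimates are unaffected; what changes is what may be concluded from them. The change should be made.

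**What to change.** In section 8.1, delete the observed-power sentence, including its closing clause on meaningful effects. Put in its place a statement about the design:

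> With 17-19 children analysed, the week-7 comparison has 80% power only for d of about 1.37-1.46 without baseline adjustment, or about 1.0-1.4 with ANCOVA at assumed baseline correlations of 0.7-0.3.

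Add a reading rule:

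> Each standardized measure is interpreted from the 95% confidence interval for d planned in section 8.2.1. Where the interval includes zero, the result is reported as inconclusive and compatible with no effect, and not as a meaningful effect missed because of sample size.

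If any power figure is kept, state its method, sidedness and covariate correlation, and reconcile it with d=0.63 and d=0.68.

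The cost is wording in section 8.1 and in the report; the intervals are already planned. The downside is a less favourable description of the standardized-measure results.

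### Section 8.1 contradicts itself: if 21, 25 and 35 per group give 80% power, the analysed 8-10 per group had about 26-44%, not under 20%, and no basis for the sizes is given

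*Combined protocol and SAP*

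**What the plan says.** Section 8.1 explains that enrolment was limited by the centre's population (40 at most) and then makes two power statements.

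- On the completed analysis: "Post-hoc power analyses indicated observed power below 20% for standardized measures due to small sample sizes". The sentence adds that this was so even though the effects were meaningful in size.
- On future studies, in three items. The first is "PROMIS Flexibility (d=0.68): 21 participants per group for 80% power", the second on the list reads "PROMIS Persistence (d=0.63): 25 participants per group for 80% power", and the last of the three is "PedsQL Social Functioning (d=0.53): 35 participants per group for 80% power".

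The other inputs are elsewhere. Section 8.3 gives the analysed size: "Sample sizes range from n=17-19 for primary ANCOVA analyses (8-10 participants per group"). Section 8.4 says "Alpha set at 0.05 for all analyses". Section 8.2.1 makes ANCOVA on the week 7 scores, with baseline as a covariate, the primary test, and promises Cohen's "d with 95% confidence intervals". It mentions one-tailed tests only under the secondary paired comparisons. Section 8.1 names no test, sidedness, baseline-outcome correlation or standard deviation behind d for either statement.

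**The concern.** Power at one sample size largely fixes power at another once the test and alpha are set. Going from 21 per group to 8-10 per group cuts the sample by a little more than half, and that is not enough to take power from 80% to under 20%. The three sizes also look small for the quoted effect sizes.

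These are the plan's only power figures, and they are offered as guidance for later trials. One statement points to 21-35 per group and the other to at least 48-55. A reader cannot tell which to use. If the quoted d values carry no further gain from the covariate, a trial built on 21, 25 or 35 per group would have 58-59% power two-sided instead of 80%.

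**Working it through.** **Inputs.** d = 0.68, 0.63, 0.53 with 21, 25, 35 per group and 80% power (8.1); alpha 0.05 (8.4); total 17-19, taken as 8+9 to 9+10 (8.3). Sidedness is not stated, so both are shown.

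**1. Can 21/25/35 be reproduced?** For an unadjusted two-sided comparison, n per group = 2(1.960 + 0.842)²/d² = 15.70/d².

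- This gives 33.9, 39.6 and 55.9, so 34/40/56. The exact t calculation gives 35/41/57 (one-sided 28/32/45).
- At 21/25/35 the unadjusted t-test has 57.6%, 58.8% and 58.9% power two-sided, and 70-71% one-sided.
- A paired t-test gives 19/22/30 two-sided or 15/18/24 one-sided.
- ANCOVA multiplies n by (1 − r²), where r is the baseline-outcome correlation. With r = 0.62 the factor is 1 − 0.3844 = 0.6156, giving 20.9, 24.3 and 34.4, which round up to 21/25/35. One-sided, r of about 0.47 does the same. Both use the normal approximation and need d to be on the unadjusted-SD scale.

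So the sizes are attainable, but only with an assumption that 8.1 does not state.

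**2. Power at the analysed size if 21/25/35 give 80%.** This check needs neither r nor the scale of d. Find the effect δ, in the metric actually tested, for which noncentral-t power is 80% at n per group. Then recompute power with noncentrality δ√(n₁n₂/(n₁+n₂)), allowing one degree of freedom for the covariate. For Flexibility at 8+9: 0.887 × √(72/17) = 0.887 × 2.058 = 1.825, which gives 39.7%.

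| Measure | δ, two-sided | Power two-sided, 8+9 to 9+10 | Power one-sided |
|---|---|---|---|
| PROMIS Flexibility (21) | 0.887 | 40-44% | 45-49% |
| PROMIS Persistence (25) | 0.809 | 34-38% | 40-44% |
| PedsQL Social Functioning (35) | 0.679 | 26-29% | 32-35% |

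Leaving out the covariate degree of freedom changes these by at most 0.3 percentage points. Even 8+8, below the stated total, gives 38%, 32-33% and 24%.

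**3. The reverse.** Two-sided power of exactly 20% corresponds to δ = 0.58 at 8+9 and 0.54 at 9+10. Those effects need 48 and 54-55 per group for 80% (one-sided 75 and 85). Power under 20% needs at least that many.

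**4. Different bases for the two statements.**

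| Sizing | Observed power | Flexibility | Persistence | Social |
|---|---|---|---|---|
| One-sided | Two-sided | 32-36% | 28-31% | 21-23% |
| ANCOVA | Unadjusted two-sided, at the stated d | 26-29% | 23-25% | 18-19% |

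Only PedsQL Social Functioning in the second row falls under 20%. On the unadjusted two-sided test, power stays under 20% only up to 6, 7 and 9 per group for the three measures.

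**The case against.** The strongest reply is that 8.1 never says the two statements share an effect and a test. The low-power sentence covers a whole battery (section 7.1.1 lists NIH Toolbox, PROMIS and PedsQL scales), while the three sizes are for selected measures under a separate lead-in. If the low power belongs to measures with smaller effects, nothing conflicts. That is possible. But the sentence is general, it refers to meaningful effects, and it runs straight into these three d values, so the natural reading is the contradictory one. If another was meant, the text has to say so.

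A second reply is that section 8.2.1 also plans paired t-tests, so the d values might be within-group while the low power is between-group. The check in step 2 assumes a two-group test and does not exclude this. A paired normal approximation gives 17.0, 19.8 and 27.9. Dividing by 0.8 for an assumed 20% attrition gives 21.2, 24.7 and 34.9, or 21/25/35 to the nearest whole number. This shows that the ANCOVA route is not the only one. It needs a paired d and an attrition allowance that 8.1 does not mention, and rounding to nearest where the usual rounding up gives 22 for Flexibility. It also sits badly with sizes quoted per group. What stands is that the source of each d should be declared before anything is recomputed.

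Third, nothing in this trial depends on these figures: enrolment was set by availability, and the observed power is post hoc. That limits the damage to guidance for later studies, but such guidance is what the three sizes are for.

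**Conclusion.** The concern holds. For the same effects and the same two-group test at alpha 0.05, 80% power at 21, 25 and 35 per group implies 40-44%, 34-38% and 26-29% at the analysed size, two-sided. A one-sided test widens the gap. Neither mixed between-group basis tried brings all three measures under 20%. The conclusion assumes that the low-power sentence covers the three listed measures and that the sizes are for a two-group comparison, as the wording suggests.

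The sizes themselves are not shown to be wrong. A common correlation near 0.62 would produce them if d is on the unadjusted-SD scale. Without covariate gain, or if d is already adjusted, the requirement is 35/41/57 two-sided. The plan should be corrected on this point, although the conduct of this trial is unaffected.

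**What to change.** State in 8.1, for each d, whether it is between-group or within-group, which analysis it came from, and which standard deviation it is scaled by. Declare one test, sidedness and baseline-outcome correlation, and recompute both statements on that basis. For a between-group d:

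- **ANCOVA gain intended, d on the unadjusted-SD scale:** state the correlation, keep 21/25/35, and correct the observed power. At r = 0.62 it is about 38-43%, 34-38% and 25-28%.
- **d taken from the ANCOVA, or no covariate gain intended:** restate the sizes as 35/41/57 per group (two-sided 5%, 80% power) and limit the under-20% statement to PedsQL Social Functioning.

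If the low power refers to other measures or other estimates, name them. If d is within-group, say so and do not present the sizes as those of a two-group comparison.

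Show each d in 8.1 with the 95% interval already planned in 8.2.1. As an illustration, an unadjusted between-group d of 0.68 at 8+9 has an interval of −0.31 to 1.65.

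The cost is a text correction, with no change to enrolment or analysis. For a between-group d on these three measures, either the quoted sizes or the quoted observed power will rise.

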8.2 Statistical Methods

8.2.1 Primary Analysis - Standardized Measures

Baseline Comparisons: Independent samples t-tests for continuous variables to assess randomization success

Primary Efficacy Analysis: Analysis of Covariance (ANCOVA)

- Independent Variable: Group assignment (IG1 intervention vs. IG2 waitlist control)
- Dependent Variables: Week 7 standardized assessment scores
- Covariates: Baseline scores, any maturation effects identified in IG2 waitlist period
- Effect sizes: Cohen's d with 95% confidence intervals

Secondary Analysis: Paired samples t-tests for within-group changes

- One-tailed tests for intervention effects (directional hypotheses)
- Two-tailed tests for control period effects

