4.2 Study Design Overview

- Phase 1: Intervention Group 1 (IG1) receives BRP intervention for 7 weeks while Intervention Group 2 (IG2) receives standard care (waitlist control)
- Phase 2: IG2 receives BRP intervention for 7 weeks while IG1 continues standard care activities
- Total study duration: 14 weeks

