5.3 Inclusion Criteria

- Children aged 24-66 months at time of enrollment
- Enrolled at YWCA Early Learning Center during study period
- Parent/caregiver consent for participation
- Ability to participate in group activities

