6.2 Standard Care Control Condition

Purpose: Control for positive researcher interaction effects while providing beneficial activities

Duration: Concurrent with BRP intervention periods **Content:** School readiness skills supplementing existing curriculum **Weekly Domains:**

- Perceptual motor skills
- Fine motor skills (tool use and coloring)
- Problem solving
- Teamwork and coordination
- Motor planning

Staffing: One licensed occupational therapist

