8.2.2 Primary Analysis - Goal Attainment Scaling

Data Conversion: Individual GAS scores converted to T-scores (M=50, SD=10)

Baseline Comparisons: Independent samples t-tests for GAS T-scores across three domains

Primary Efficacy Analysis: ANCOVA comparing IG1 (weeks 0-7) vs. IG2 (weeks 7-14)

- Covariates: Baseline domain differences, IG2 control period changes
- Combined score calculated by averaging three domain T-scores

Secondary Analysis:

- Within-group paired samples t-tests for intervention effects
- Maintenance analysis for IG1 (weeks 8-14)
- Clinical significance threshold: 10+ T-score point improvements

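### The primary week-7 ANCOVA adjusts for an undefined, data-dependent maturation term that, on its natural reading, is built from the control arm's own week-7 outcome

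*Combined protocol and SAP*

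**What the plan says.** Section 8.2.1 sets out the primary efficacy ANCOVA for the standardised measures. The outcome line reads "Dependent Variables: Week 7 standardized assessment scores", the factor is group (IG1 on BRP against IG2 on the waitlist), and the adjustment line reads "Covariates: Baseline scores, any maturation effects identified in IG2 waitlist period". No section defines the second covariate, gives its value for IG1 children, or says what makes an effect identified.

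Four other places bear on its meaning:

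- Section 4.2 fixes the waitlist window as Phase 1: "Intervention Group 1 (IG1) receives BRP intervention for 7 weeks while Intervention Group 2 (IG2) receives standard care (waitlist control".
- The schedule in section 7.2 gives "All standardized measures, initial GAS" at week 0, then the standardised measures at week 6/7 and week 14. Only the first two fall in the waitlist window.
- Section 8.2.2 has a parallel line for Goal Attainment Scaling: "Covariates: Baseline domain differences, IG2 control period changes".
- The secondary analyses in section 8.2.1 include "Two-tailed tests for control period effects". This is the only listed test that could identify an IG2 waitlist effect, but the plan does not link it to covariate entry.

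**The concern.** With only two assessments in the window, a maturation effect on a standardised measure in IG2 can only be that arm's week-7 score minus its baseline. Section 8.2.2 points the same way. Such a term arises after randomisation, is computed from the dependent variable, does not exist in IG1, and enters or stays out according to the results. Nor is it maturation alone. During the waitlist period IG2 receives an activity programme whose stated purpose is "Control for positive researcher interaction effects while providing beneficial activities".

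This is the primary model for every standardised measure, and a statistician could not program it from the text. Sections 8.1 and 8.3 already report effect sizes, post-hoc power and analysed numbers, and section 8.1 sizes future studies from those effects. A reader cannot establish whether the term was in the model behind them.

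**Working it through.** **Inputs from the plan.** 17-19 children per ANCOVA, 8-10 per group (section 8.3); alpha 0.05 (section 8.4); d = 0.68 and 0.53 (section 8.1).

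**Assumptions not in the plan.** SD 10; baseline to week-7 correlation 0.6 (range 0.4-0.8); maturation of 1, 2, 3 or 5 points, equal in both arms; two-sided tests; entry when IG2's two-tailed paired p<0.05.

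**Step 1: is the term needed?** Write Y = rB + m + τG + e, with B the baseline score, G = 1 for IG1 and m the shared maturation. The baseline-adjusted difference between arms is (m + τ) − m = τ, so m cancels. In simulation (20,000 replicates per scenario) the baseline-only ANCOVA has bias within 0.06 point and rejects in 4.7-5.4% of null trials at every maturation tried.

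**Step 2: what each coding does.**

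1. *IG2's mean change c as a group-level value.* The column is c(1 − G) = c − cG, a combination of the intercept and group columns. The design has rank 3 with 4 columns, so the group effect is not estimable.
2. *Each IG2 child's change, IG1 set to 0.* The group coefficient now compares IG1 with a hypothetical IG2 child who did not change. Most of the shared maturation is therefore credited to BRP.
3. *Each child's own change in both arms.* Y = B + (Y − B) exactly, so the fitted coefficients are 1 for baseline, 1 for change and 0 for group, whatever the true effect. A simulated true effect of 6.8 returns 0 to machine precision.

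Codings 1 and 3 follow from algebra and need none of the assumptions above.

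**Step 3: size under coding 2** (9 per arm, correlation 0.6, no true effect):

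| Maturation | Term entered | Bias, conditional entry | Type I error | Bias, always entered | Type I error |
|---|---|---|---|---|---|
| 1 | 6.5% | +0.22 | 3.9% | +0.90 | 6.3% |
| 2 | 8.9% | +0.44 | 4.0% | +1.75 | 8.4% |
| 3 | 14.0% | +0.80 | 4.3% | +2.63 | 12.7% |
| 5 | 31.6% | +2.11 | 8.0% | +4.40 | 23.5% |

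The conditional column can be checked by hand. At 5 points, triggered trials average −2.40 baseline-only and 4.38 with the term, a shift of 6.78; 0.316 × 6.78 = 2.14, against 2.11 simulated.

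A second simulation (6,000 replicates, SD units) agrees. At 0.5 SD, conditional bias is 0.22 SD with 8.4% error, and always-entered bias is 0.44 SD with 23.0% error.

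**Step 4: relative to the plan's effects.** If d is in baseline-SD units, 0.68 and 0.53 are 6.8 and 5.3 points. At 2 points of maturation the conditional bias is 0.44/6.8 = 6% to 0.44/5.3 = 8% of the effect. At 5 points it is 2.11/6.8 = 31% to 2.11/5.3 = 40%.

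**Step 5: sensitivity at 5 points, conditional entry.** Across the 8-10 group sizes at correlation 0.6, bias is +1.9 to +2.3 and type I error 6-11%. Over correlations 0.4-0.8, bias is +1.6 to +3.5 and error 6-26%.

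**Step 6: same data, three answers.** With 9 per arm, true effect 6.8 and maturation 5, in trials where the term is triggered, baseline-only averages 4.4, coding 2 averages 11.2 and coding 3 gives 0. Baseline-only is itself low here because the term is triggered when IG2 happened to improve. Against the truth, coding 2 is off by 11.2 − 6.8 = +4.4.

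**The case against.** The strongest reply is that the size of harm is assumed. The SD, correlation, maturation, IG1 coding and p<0.05 trigger are not in the plan. Under conditional entry, type I error is about 4% up to 3 points of maturation; clear inflation needs 5 points, half an SD in seven weeks. That stands, so the magnitude figures are scenarios, not the basis of the finding.

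The direction is not settled either. If an analyst instead subtracted IG2's mean change from IG1's scores whenever it was significant, bias would run against BRP: −0.27 SD at 0.5 SD of maturation, with 26% rejection under the null. That is not a covariate adjustment, so it is not what section 8.2.1 describes, but upward bias should not be presumed.

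If the non-zero d values in section 8.1 came from this ANCOVA, which is not stated, codings 1 and 3 cannot have produced them. Baseline-only and coding 2 both remain possible, and they can differ materially.

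Two readings are harmless. If no maturation was identified, the model is the ordinary baseline-adjusted ANCOVA. If a pre-randomisation variable such as baseline age was meant, entered for every child, the analysis is valid; section 5.3 gives a wide range, "Children aged 24-66 months at time of enrollment". The text states neither. Pilot status does not remove the problem, because section 8.1 uses these effect sizes to plan further trials.

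**Conclusion.** The concern holds, with high confidence. The covariate is undefined, its inclusion depends on the results, and the only standardised data that could supply it include the control arm's week-7 outcome. The collinearity under coding 1 and the forced zero under coding 3 are exact. The bias under coding 2 is scenario-dependent: modest on average under conditional entry up to 3 points, and about +2 points with 6-11% type I error at 5 points and correlation 0.6. The reason to correct it is that the primary model cannot be reproduced and, once the term is triggered, gives a biased, null or non-estimable group effect under the codings examined, while baseline adjustment alone is valid throughout.

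**What to change.** - Remove the maturation term from the covariate line in section 8.2.1. Fit week-7 score on group and the same measure's baseline score.
- Report IG2's waitlist change descriptively, separately from the efficacy model.
- For each measure already analysed, state whether the term was entered, what triggered it and how IG1 was coded. Re-run without it and show both results.
- If a maturation covariate is wanted, name a pre-randomisation variable such as baseline age and enter it for every child, whatever IG2's results.

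The cost is a change of wording, a disclosure and a re-run on data already collected; deleting the term costs no degrees of freedom. The optional age covariate, if unrelated to outcome, lowers power at 9 per arm from about 37% to 35% at d = 0.68 and from 25% to 23-24% at d = 0.53. It costs less, or gains power, if age predicts the score.
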